# **Assays**

• Assays will be processed by the Core Laboratory at the Yale Center for Clinical Investigation. These include leptin, ghrelin (octanoylated and des-octanoylated), and estrogen/progesterone. Samples will be stored in -70 freezer, and batched for processing. Medication levels will be processed and stored in a -70 freezer until sent to World Wide Clinical Trials for analysis.

**Assessment Training:** Independent outcomes assessors will be trained in the study interviews by investigators following well-established protocols from previous grants. Once interviewers are certified in the measures they will receive ongoing supervision to ensure consistent use and prevent drift. [name] will do inter-rater reliability studies, as before for BED ([name] et al., 2004) and psychiatry (Zanarini et al., 2000).

Maintenance of Cohort. Research staff will form on-going relationships and maintain contact with participants. Our experience indicates this improves likelihood of participants' willingness to perform follow-up assessments. In addition: (1) At pre-screening and baseline assessment, participants will be asked whether they will be available for the entire study duration; (2) Participants will be excluded if unable to comply with birth control methods; (3) Participants will provide names and contact information of at least two relatives or friends and permission to contact them if they move without notifying investigators; (4) At each assessment, participants will be asked if they have plans to move; and (5) We will reimburse participants for completion of the assessments.

- 5. Genetic Testing N/A ⊠
- 6. **Subject Population:** Provide a detailed description of the types of human subjects who will be recruited into this study.
  - Two hundred (N=200) participants with BED with and without obesity (n=100 and n=100, respectively), and meeting other eligibility criteria as described below, will be randomized to participate in this trial. Previous work with this population suggests participants will be adults, male and female, and represent diverse racial/ethnic and sociodemographic groups.
- 7. **Subject classification:** Check off all classifications of subjects that will be specifically recruited for enrollment in the research project. Will subjects who may require additional safeguards or other considerations be enrolled in the study? If so, identify the population of subjects requiring special safeguards and provide a justification for their involvement.

□Children	☐ Healthy	☐Fetal material, placenta, or dead fetus
□Non-English Speaking	☐ Prisoners	☐Economically disadvantaged persons
□Decisionally Impaired	☐ Employees	□Pregnant women and/or fetuses
□Yale Students 図N/A	☐ Females of childbearing pote	ential
NOTE: Is this research proposal des Yes □ No ☒	igned to enroll children who are	wards of the state as potential subjects?

8. Inclusion/Exclusion Criteria: What are the criteria used to determine subject inclusion or exclusion?

### Inclusion Criteria:

- (1) 18 to 70 years old;
- (2) Meet DSM-5 criteria for BED based on semi-structured diagnostic interview (EDE);
- (3) BMI in the obesity (BMI >30 and <50) or non-obesity (BMI >21.5 and <29.9) range;
- (4) Available for the duration of the treatment and follow-up (15 months).
- (5) Read, comprehend, and write English at a sufficient level to complete study-related materials.
- (6) Provide a signed and dated written informed consent prior to study participation.

### Exclusion criteria:

Main exclusion criteria reflect primarily clinical or medical issues that would indicate different treatment needs or contraindication to NB medication.

- (1) Predisposition to seizures (e.g., history or evidence of seizure disorder, febrile seizures during childhood, brain tumor, cerebrovascular disease, or significant head trauma; family history of idiopathic seizure disorder, or is currently being treated with medications or treatment regimens that lower seizure threshold).
- (2) Lifetime anorexia or bulimia nervosa, or currently regularly self-inducing vomiting.
- (3) Co-existing psychiatric condition that requires hospitalization or more intensive treatment (e.g., bipolar mood disorders, psychotic illnesses, severe depression).
- (4) Currently taking a medication that is a contraindication to NB medication (MAOI, opiates, benzodiazepines, CYP2B6 inhibitors, bupropion, naltrexone).
- (5) Positive urine drug screen for opiates.
- (6) History of allergy or sensitivity to bupropion or naltrexone.
- (7) Serious uncontrolled medical conditions (including renal or hepatic impairment, neurological, chronic pulmonary disease, or any other serious, unstable medical disorder).
- (8) Breast-feeding or pregnant.
- (9) Uncontrolled hypertension with a seated systolic blood pressure > 160 mmHg, diastolic blood pressure > 100 mmHg, or heart rate > 100 beats/minute.
- (10) Previous surgical or device intervention for obesity within the past 5 years.
- (11) Have not donated blood for 6 weeks prior to the study and agree not to donate blood for 8 weeks following their participation.
- (12) History of congenital heart disease, cardiovascular disease, cardiac arrhythmias requiring medication, atherosclerotic disease, or a history of cerebrovascular pathology including stroke.
- (13) Current uncontrolled Type I or Type II diabetes mellitus.

- (14) Untreated hypothyroidism with a TSH > 1.5 times the upper limit of normal for the test laboratory with repeat value that also exceeds this limit.
- (15) Untreated gallbladder disease.
- (16) Current or recent (within 12 months) drug or alcohol dependence
- (17) Currently receiving effective treatment for eating or weight loss.
- (18) Currently participating in another clinical study in which the participant is or will be exposed to an investigational or a non-investigational drug or device.
- (19) Reports active suicidal or homicidal ideation.

### Biosensor Arm:

### Inclusion Criteria:

- (1) 18 to 70 years old.
- (2) Willing to wear the Garmin band and interact with the app daily for 6 weeks.
- (3) Read, comprehend, and write English at a sufficient level to complete study-related materials.
- (4) Provide a signed and dated written informed consent prior to study participation.

### Exclusion criteria:

- (1) Co-existing psychiatric condition that requires hospitalization or more intensive treatment (e.g., bipolar mood disorders, psychotic illnesses, severe depression).
- (2) Serious uncontrolled medical conditions (including renal or hepatic impairment, neurological, chronic pulmonary disease, or any other serious, unstable medical disorder).
- (3) Breast-feeding or pregnant.
- (4) Previous surgical or device intervention for obesity within the past 5 years.
- (5) Currently receiving effective treatment for eating or weight loss.
- (6) Current uncontrolled medical condition or medication that could impact weight or eating behavior.
- (7) Currently participating in another clinical study in which the participant is or will be exposed to an investigational or a non-investigational drug or device.
- (8) Reports active suicidal or homicidal ideation.
- 9. How will **eligibility** be determined, and by whom? Write here

Participants will be interviewed by a trained research clinician (MINI and EDE) to determine whether they meet criteria for binge-eating disorder. These diagnostic clinical interviews will also determine whether participants have any co-existing psychiatric conditions (including substance use disorders) that require hospitalization or more intensive/different treatment.

The study physician will determine medical eligibility based on results of participants' physical examination (within one year of starting the study), as well as results of the baseline assessment and blood/urine testing. Information obtained from the physical examination will include a list of current medications, which participants will be asked to bring to their baseline assessment.

**Biosensor Arm:** Eligibility is determined by trained research clinicians. Physical exam and blood/urine testing are not required since the Biosensor is non-invasive and there is no medication administered.

10. **Risks:** Describe the reasonably foreseeable risks, including risks to subject privacy, discomforts, or inconveniences associated with subjects participating in the research.

# NB Pharmacotherapy.

Since participants will undergo a thorough physical evaluation and screening for known contraindications for treatment with the NB medication, potential risks will be minimized. In clinical trials, NB was associated with the following side effects in 10% or more of the time and significantly greater than rate in placebo: nausea, headache, constipation, and vomiting. NB was associated with the following side effects less than 10% of cases but significantly more than placebo: dizziness, insomnia, dry mouth, and diarrhea. Large studies (e.g., Greenway et al., 2010 with N=1742) reported that the proportion of participants reporting a serious adverse event did not differ between NB and placebo (1.6% versus 1.4%) and that none of the observed events were judged to be related to the study. It appears important to evaluate and monitor blood pressure and heart rate because studies have found that patients with obesity treated with NB have significantly lower drops than placebo in systolic BP changes (-0.4 vs. -2.1), diastolic BP (-0.1 vs -1.0), pulse rate (1.0 vs -0.1) (Greenway et al., 2010).

### Pill Placebo.

The main risk associated with placebo is failure to improve, although some persons do improve solely on placebo. Although the placebo is inactive, some persons who take the placebo report that they experience some of the side-effects listed above.

#### Assessments and Interviews.

Participation of the human laboratory component does not add risk above that associated with the clinical trial, with the exception of repeated blood drawing. Risks will be minimized by using trained research nurses. Further, subjects have not donated blood for 6 weeks prior to the study, and they are informed to not donate blood for 8 weeks following their participation.

Participation in the biosensor component does not add risk. De-identified biosensor and smartphone data will be remotely collected by mHealth Core Facility at UMass for data processing.

Research assessments are all noninvasive, and add no substantial risk. The major disadvantages are the time taken to complete them and possible breach of confidentiality. Our past experience with these measures indicates that they are acceptable to participants. Careful efforts aimed at maintaining confidentiality will be made. All identifiable information will be stored in a locked research cabinet. All participants will be assigned a study participant number. A list of numbers and the corresponding names will be maintained by the Principal Investigator and stored in a locked research cabinet. Any identifying information that is collected will be kept in a locked research cabinet in a locked unit. Any information published as a result of the study will be such that it will not permit identification of any participant. All information collected will remain confidential except when we are legally required to disclose such information by law. These circumstances include knowledge of abuse of a child or elderly person, threats of harm to self or others, and plans to harm to property. Data will be stored in locked cabinets for 7 years after the final data are collected. Research records may be the subject of an audit by a regulatory agency within the federal government. Organizations which have a responsibility for protecting human subjects, including the Yale IRB (Human Investigation Committee), may have access to the research records. Additionally, the funding agency (NIH) may have access to the research records. The participant's identity will remain protected except as required for legal or regulatory inquiries. Individually identifiable health information will be protected in accordance with the Health

Insurance Portability and Accountability Act of 1996. All research personnel will be trained on IRB, ethics, and HIPAA procedures.

There is the possibility that drawing blood might cause a small bruise, mild discomfort, or infection.

### Failure to Improve.

There is a chance that the patient's binge eating or obesity may fail to improve or may worsen during the study.

### Biosensor- Physical Discomfort from Wristband.

As part of the study, subjects will wear a Garmin wristband and carry a smartphone for the collection of data. While there is potential physical discomfort associated with regular wearing of a wristband, our experience suggests that this has been minimal and subjects have been comfortable wearing the device for extended periods of time. The wristband is adjustable.

### Biosensor – Android Cell Phone App

All information collected from both the Garmin wristband and the Android cell phone app will be deidentified. The data from the bands in continuously transmitted o the mHealth Core Facility at UMass through the Garmin service for Academic Researchers. The data from the Android cell phone app will be collected, transmitted, and stored by the mHealth Core Facility at UMass and provided to Yale.

### **Data Security and Collection.**

Security of user information is of paramount importance to us. We have completed a Security Design Review (INC1917498) through Yale ITS and have received approval using this technology (HIC# 2000023970, [name][PI]). Security of user information is of paramount importance to us. We work to protect security of sensitive information during transmission by using Secure Socket Layer (SSL) software, which encrypts information that is input. Our servers are behind a firewall, and we secure it using the best available methods. This data will not be associated with any personal information of the participant; rather, it will only be associated with a random key associated with the phone. The study organizers at Yale will keep a mapping between the random key and the identity of the individual. We will include privacy safeguards to ensure that participants are comfortable with the data they are revealing. The user will be asked to specify privacy zones where they do not with GPS information to be recorded. This can be done at any point during the study by contacting study organizers or they can explicitly turn on or off GPS logging by using the Settings screen on the app. During periods when location logging is enabled, the system will automatically upload location data to a secure backend database.

We note that [name] has recently completed an NIH R01 (DA033733-01) where we monitored cocaine addicts in out-patient settings with several on-body sensors (wristband, chestband, and smartphone), which had even more extensive data collection than we are proposing in this grant (we collected GPS, respiration, ECG, phone usage patterns, and other signals in the R01 effort). They are also part of several other efforts with similar data collection considerations (NSF 0910706 and NIH 1-U54EB020404-01). Hence, we have extensive experience in mitigating the potential risks, and privacy issues associated with the collection of, and use of sensitive on-body sensor data. Given our experience in this domain, we will follow all the best practices in acquisition and management of subjects' private data.

11. Minimizing Risks: Describe the manner in which the above-mentioned risks will be minimized.

Effective screening will exclude all prospective participants who would be at greater risk for complications because of medical or psychiatric illnesses. Subjects will be evaluated repeatedly throughout the study and will be monitored for any adverse reactions. Given the uncertain effects of medication during pregnancy, the following precautions will be taken for women of reproductive age: 1) a female participant of reproductive age must agree to use a reliable method of birth control while she is in the study and to alert the research team if she departs from her birth control plans or if, in spite of adherence to these plans, she thinks she might be pregnant; we will do a urine pregnancy test as needed during the treatment phase of the study, and 2) if a woman becomes pregnant after study entry, her medication will be discontinued.

Screening for opiate use and warning about opioid withdrawal. During the screening process, we will conduct urine drug screens for opiate use as part of the medical evaluation if patients report a lifetime history of substance use disorder with opiates, or if patients report any use of opioid-based pain medications within the past 6 months. Additionally, we will include this advisory pertaining to opioid use and examples of opioid-based medications and drugs in the written consent form as well as the verbal consent process: Naltrexone can cause withdrawal symptoms in individuals who are taking opioid pain medications or drugs. You should not participate and we will not include you in the study if we know or suspect you are using opiate-containing drugs.

Monitoring weight loss. Participants who have a BMI in the healthy-weight or overweight range (i.e., BMI 21.5-29.9 kg/m²) will be monitored closely for changes in weight. If any participant's weight drops below 20.0 kg/m² over the course of the study, this will trigger a discussion amongst investigators and the study physician. Research clinicians will review and/or assess eating behaviors to ensure the patient is not vomiting. This will be discussed with the team along with any reported side effects, and whether the treatment should continue per protocol, dosage decreased, or medication stopped will be considered. We anticipate this will be a rare occurrence; however, the use of this "early signal" (i.e., weight below 20.0 kg/m²) will greatly reduce the likelihood of adverse events.

Monitoring depressive symptoms. Depressive symptoms will be monitored frequently. To monitor changes in depressive symptoms, patients will be asked to complete the BDI-II at all clinic visits (2x in first month, monthly thereafter). Research clinicians will review BDIs during the clinic visit, and will asked pointed questions pertaining to suicidality/suicidal ideation using the Columbia Suicide Severity Rating Scale. If it appears, based on the clinical judgment of the research clinician, that the participant is experiencing significant adverse effects of the medication, the investigators and study physician will be consulted and a determination of whether to discontinue the medication will be made. The participant will be compensated in full, and will be asked to continue to attend clinic visits and to continue to participate (if applicable) with the behavioral support to ensure remission of any distressing symptoms. If warranted, the participant will be given a referral. There is no assessment of suicidality in the Biosensor Arm.

Blood pressure and heart rate will be measured during all evaluation visits. Two readings will be taken at each assessment. In the event of systolic blood pressure  $\geq 160$  mm Hg and/or diastolic blood pressure  $\geq 100$  mm Hg, or an increase in heart rate of  $\geq 15$  bpm (from baseline), the study physician will be notified and will determine whether additional intervention and/or medication discontinuation is warranted.

Liver function will be measured during baseline, at month-1 clinic visits, and at the end of treatment. The study physician will review results of a full hepatic panel prior to the start of treatment and throughout treatment. Participants with hepatic disease will be excluded if this is detected at baseline, per exclusion criteria. Any changes and out-of-range values will be flagged immediately by research clinicians, and the study physician will determine whether additional intervention and/or medication discontinuation is warranted.

Wallet Safety Card. Each participant will be given a wallet card with the code number for the medication assignment in the event of an emergency and the need for breaking the blind. The research pharmacy has 24-hour service. Participants will be provided with contact information for the study physician and the PI, as well as emergency numbers in case of adverse events or other concerns. Research staff will have cell phones and can be reached 24/7.

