**Baseline Assessment**: Participants will complete a physical exam, vitals, and routine laboratory blood work (including lipid profile, Hb1Ac, and liver function tests) at which time the study physician will review the subject's medical status and medical eligibility criteria. Patients will also have a urine screen for opiates. As part of the determination of eligibility, participants will complete two interviews, the MINI International Neuropsychiatric Interview-Version 7.0 (MINI) and Eating Disorder Examination (EDE) to generate psychiatric

diagnoses and detailed current eating disorder features and diagnoses. Other measures, for safety and establishment of baseline values, will also be obtained: BMI, vitals, eating behaviors, mood, and quality of life.

For a full description of instruments, see "Measures," which includes a grid depicting when each measure is administered. The baseline assessment will occur over 1-2 in-person meetings and is estimated to take a total of 2-3 hours in-person.

Randomization. Eligible participants who agree to participate and provide written informed consent will be randomized in equal proportions to one of the two treatments (using blocked randomization with random block sizes of 4 and 8 to obviate any secular trends). Gender will be balanced across cells (60% female). We will monitor randomization procedure and determine whether any systematic differences in demography (age, ethnicity/race) or clinical characteristics (psychiatric co-morbidity) become evident. We will consider adjustment to randomization if indicated (Kraemer & Fendt, 1990; Kraemer & Pruyn, 1990). The Biostatistician, [name], will be responsible for developing the randomization schedule in conjunction with the Investigational Drug Pharmacy (IDS), at Yale-New Haven Hospital. The IDS will randomize participants to medication groups. Research study staff (clinicians and outcomes assessors) and participants will all remain blind to the medication condition.

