### Measures:

### **Screening Measures**

- MINI International Neuropsychiatric Interview-Version 7.0 (MINI) [57] is a brief structured interview for Axis I psychiatric disorders. Validation and reliability studies have supported the MINI, including good convergence with SCID [57]. The MINI requires much less time than the SCID and reduces participant burden while providing adequate psychiatric data to characterize patients and determine exclusion criteria.
- Eating Disorder Examination Interview—16th Edition (EDE) [58] is an investigator-based interview assesses the features of eating disorders and generates eating disorder diagnoses. The EDE will be our primary method for assessing binge eating and eating disorder psychopathology. The EDE focuses on the previous 28 days, except for diagnostic items, which are rated for additional duration stipulations to address *DSM*-5 criteria for BED. The EDE assesses the frequency of different forms of overeating, including objective binge-eating episodes (OBE; i.e., unusually large amounts of food with loss of control). The EDE also comprises four scales (dietary restraint, eating concerns, weight concern, and shape concern) and a global severity score. The EDE has good psychometric properties [59], is the major outcome measure for BED RCTs [44, 60], and has good test-retest reliability.
- Body Mass Index (BMI) will be calculated using measured Height (measured once at baseline) and Weight (obtained regularly at assessment meetings).
- Lipid profiles (**Lipids**): total cholesterol, HDL-, LDL-cholesterol, triglycerides will be obtained fasting per established protocols (Anderson et al., 1995).
- Glycemic Control: HbA1c, Glucose and Mean Plasma Glucose, routine measures of average glucose control for a previous (3-month) period.
- Hepatic function panel (**Liver Function**) will be assessed for safety at the first monthly treatment visit and at the end of treatment.
- Thyroid-stimulating hormone (TSH) will be assessed if patients report any history of thyroid disease or are taking thyroid medications.
- Urine drug testing for opiates will be completed for all participants.
- Urine pregnancy testing will be assessed for female patients of child-bearing potential.
- Menstrual Cycle Data: Menstrual cycle calendar (updated regularly), hormone use, reproductive and gynecological status

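### The urine opiate screen is required for all participants in one section and tied to self-reported opioid history in another

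*Combined protocol and SAP*

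**What the plan says.** The test appears in several places in the combined protocol and SAP.

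- **Baseline Assessment** (Section I, item 4): "Patients will also have a urine screen for opiates". No condition is attached.
- **Figure 2, assessment grid**: the opiate test is listed under Safety Measures with a mark at baseline and no qualifier.
- **Measures, Screening Measures**: "Urine drug testing for opiates will be completed for all participants".
- **Section I, item 8, exclusion (5)**: a positive opiate screen excludes the person.
- **Section I, item 9**: the study physician's medical eligibility decision draws on the urine results.
- **Section I, item 11 (Minimizing Risks)**, paragraph on opiate screening: the protocol describes "urine drug screens for opiate use as part of the medical evaluation if patients report a lifetime history of substance use disorder with opiates". It then gives a second trigger, which is recent use of opioid painkillers as reported by the participant.

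The item 11 paragraph also names the hazard: "Naltrexone can cause withdrawal symptoms in individuals who are taking opioid pain medications or drugs". Its consent advisory adds: "You should not participate and we will not include you in the study if we know or suspect you are using opiate-containing drugs".

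**The concern.** One section makes the test universal. Another ties it, at the same stage of the study, to what the participant chooses to report. The test guards against opioid withdrawal brought on by naltrexone, and the people it most needs to find are those who do not disclose opioid use. Under the item 11 wording, those people trigger no test.

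Two things are at stake. The first is safety before the first dose. The second is even application of exclusion (5), which cannot operate where no result exists. There is also an audit problem. Item 12 calls for regular review of adherence to the eligibility criteria, yet a missing opiate result is a deviation under Screening Measures and compliant under item 11.

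**Working it through.** No arithmetic decides this point. It rests on setting the passages side by side.

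**1. Is it the same test at the same stage?** Yes. Item 11 places the screen within the screening process and the medical evaluation. The Baseline Assessment section places it in the baseline medical work-up, where the study physician reviews eligibility. Item 11 does not describe its test as a repeat or an addition.

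**2. Is the universal wording deliberate?** It appears so. Other tests in the same Screening Measures list carry limits. TSH "will be assessed if patients report any history of thyroid disease or are taking thyroid medications". For pregnancy: "Urine pregnancy testing will be assessed for female patients of child-bearing potential". The opiate line has no such limit and says all participants. Figure 2 likewise marks TSH as done when needed but puts no qualifier on the opiate test. The pregnancy test shares that row, also unqualified, so the grid supports this reading without settling it.

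**3. Does the Biosensor Arm explain the condition?** No. Item 9 exempts that arm from urine testing because it involves no medication. The item 11 paragraph concerns people who may receive naltrexone.

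**4. What follows under each rule?**

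| Rule followed | Who is tested before dosing | Exclusion (5) |
|---|---|---|
| Baseline Assessment, Figure 2, Screening Measures | All randomized participants (planned N = 200) | Can be applied to everyone |
| Item 11, read as a condition | Only those reporting one of the two histories | Cannot be applied to the rest |

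**5. Does another step close the gap?** Not fully. Exclusion (4) covers opiate medication and exclusion (16) covers current or recent drug dependence. The MINI, the physician's review and the consent advisory also help. These rest largely on disclosure, and the urine screen does not. The pre-treatment laboratory session is no substitute: Table 1 lists a urine pregnancy screen there but no opiate test, and participants may decline the session.

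**6. How many people are affected?** This cannot be computed. The documents give no proportion reporting either history, no rate of undisclosed opioid use and no detection rate for the test. The design assigns 2 cells × 50 = 100 of 200 participants to active drug. That is the number exposed to naltrexone, not the number affected by the inconsistency.

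**The case against.** The strongest reply is that there is no strict contradiction. Item 11 says the test is done if a history is reported, not only if, so testing everyone satisfies every section. The baseline procedure, the assessment grid and the measure definition all point to universal testing, and exclusion (5) presumes a result. Staff running a baseline visit would naturally work from those, and physician review of baseline results is already in the plan. The medication list is not purely self-report either: item 9 presents it as information from the physical examination, although participants are asked to bring it.

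Much of this stands. Universal testing is the better-supported rule and probably the intended one, and nothing in the text tells staff to omit a test. But if everyone is tested regardless, the two triggers in item 11 do nothing. The natural reading of a rule to test when a history is reported is that others are not tested. Item 11 is also the protocol's direct answer on how risks are minimized, so staff or the IRB may well consult it. The objection limits the likely consequence but does not remove the conflict.

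**Conclusion.** The concern holds. The explicit conflict is between Screening Measures, which covers all participants, and item 11, which ties the same test to two reported histories. The Baseline Assessment section, Figure 2 and exclusion (5) support the universal rule. No section says which governs.

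The practical consequence depends on an assumption: that some staff would read item 11 as limiting who is tested. If none do, there is no gap. If some do, a participant who does not disclose opioid use could be given naltrexone without a urine test. No count or probability of harm can be given from the documents. The issue concerns safety and eligibility, with no effect on alpha, power or sample size. It should be corrected because the ambiguous sentence sits in the section meant to control this risk.

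**What to change.** Amend the opiate-screening paragraph in Section I, item 11 to say that every participant in the medication trial has a urine opiate screen at baseline and that the study physician reviews the result before the first dose. Keep the two reported histories only as grounds for additional review or a repeat screen. This brings item 11 into line with the Baseline Assessment section, Figure 2, Screening Measures, exclusion (5) and item 9.

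The cost is a one-sentence amendment. The baseline test and the physician's eligibility review are already in the plan, so no new procedure is needed; a repeat screen would arise only where a reported history prompts it.
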